10.2.2.2 Psychological Risks and Mitigation

Mild anxiety and depressed mood are occasionally reported 1 to 3 days after MDMA administration [49, 110]. Psychological distress from MDMA could arise from the first indications of MDMA effects until the last effects have dissipated or even later. Anxiety or distress during the session may last for as little as 5 minutes or for as long as 5 hours or more. In addition, psychological distress could arise following an Experimental Session as a result of participants having difficulty integrating their experience after the MDMA effect has subsided. In previous Phase 1 and Phase 2 studies, these symptoms have been self-limiting and have responded well to reassurance from the therapy team, with occasional use of benzodiazepines for anxiety. In this study, participants will have the intention of confronting and working through traumatic experiences. Accordingly, signs of psychological distress, panic, or other unpleasant psychological reactions are to be expected and may be considered an element of the psychotherapeutic process.

Proper preparation and follow-up support will reduce the difficulties participants might have with acute or sub-acute reactions. The potential for destabilizing psychological distress will be minimized by:

- Excluding people who might be more vulnerable to it (such as people diagnosed with bipolar affective disorder type 1 or with psychotic disorders).
- Preparatory Sessions of non-drug psychotherapy before the Experimental Session.
- Creating an atmosphere of trust during the Experimental Session.
- Close monitoring.
- Phone contact with participants during the week after the Experimental Session.
- Integrative Sessions.
- Overnight stays at the study site for the night of each Experimental Session. Qualified personnel will be available during the overnight stay to respond to the needs of the participant. Attendants will be instructed to contact the therapy team upon request or at the appearance of signs of a potential Serious Adverse Event.

During the Preparatory Sessions, participants will be made aware of the fact that difficult emotions, including grief, rage, fear, or panic, may arise during Experimental Sessions. Every effort will be made to help participants resolve difficult symptoms and to arrive at a more comfortable and relaxed state by the conclusion of the Experimental Session, including empathic listening on the part of the therapy team and performance of diaphragmatic breathing by participants.

If the participant is severely agitated, anxious, in danger of self-harm or suicide, or is experiencing any other severe psychological distress, at the end of a psychotherapy session, at least one member of the therapy team will remain with the participant for at least 2 more hours. During this time, the therapy team will employ affect management techniques, will talk with the participant to help them gain cognitive perspective of their experiences, and will help the participant implement the self-soothing and stress inoculation techniques presented during the Preparatory Sessions. If the participant remains severely anxious, agitated, in danger of self-harm

or suicide, or is otherwise psychologically unstable at the end of the 2-hour stabilization period, the site physician and therapy team will decide between the following options:

1. If severe distress occurs at the end of an Experimental Session, a psychiatric nurse, therapeutic assistant, physician, or therapy team member will stay with the participant until the severe distress resolves or until the time of their Integrative Session appointment the following morning. The therapy team will then meet with the participant daily until the period of destabilization has passed.
2. If the participant experiences severe, persisting emotional distress, such as panic attacks, severe generalized anxiety, or insomnia following an Experimental Session, a licensed therapy team member or the site physician may prescribe a benzodiazepine (specifically, lorazepam) and/or sleep aid (e.g., zolpidem). The route, frequency, and dose should be determined by the site physician. If these medications are stocked on site, they should be stored according to applicable national and local regulations. This medication will be captured on the Concomitant Medications eCRF. The site physician should not prescribe an SSRI, SNRI, or monoamine oxidase inhibitor (MAOI) in this context, unless it has been determined that the participant will be withdrawn from the study. Residual symptoms will be addressed during the frequent follow-up psychotherapy visits with the therapy team.
3. If a participant should become psychotic, arrangements will be made to stabilize them or transfer them to the ED if hospitalization is necessary. Any participant who is hospitalized after a severe psychological reaction will be suspended from the protocol until after recovery or stabilization, at which time the investigator and/or site physician will carefully evaluate the participant's emotional status.

For those participants engaged in an ongoing therapeutic relationship with a psychotherapist or psychiatrist, the participant's outside therapist(s) will be involved in the management of any psychiatric complications. For those participants engaged in an ongoing psychotherapeutic relationship with the investigator or member of the therapy team, the management of any psychiatric complications will be undertaken by them in their capacity as the participant's therapist.

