2.2.2 MDMA

MDMA is a ring-substituted phenylisopropylamine derivative invented by the Merck pharmaceutical company in 1912 [20, 21]. Similar to SSRIs, MDMA binds to the serotonin transporter, but has additional effects on carrier-mediated release and reuptake inhibition of norepinephrine, and to a lesser extent in humans, dopamine [22-28]. MDMA also increases levels of affiliative neurohormones oxytocin and vasopressin, which increases trust and attenuates reactivity to threatening cues, and some researchers have suggested a role for oxytocin in treating PTSD. The indirect effects of MDMA on central and peripheral neurohormone release contribute to a novel mechanism that may help regulate the HPA axis, which would treat the core psychopathology of PTSD for a durable remission.

Onset of MDMA effects occurs ~0.5 to 1 hour after oral administration, and peak effects occur 1.25 to 2 hours after the initial dose. Effects of the initial dose last 3 to 6 hours, which is extended to 5 to 8 hours with a supplemental half-dose administered 1.5 to 2 hours post initial dose. Orally administered doses of MDMA have a half-life of 7 to 9 hours in humans. Unlike approved PTSD medications, therapeutic effects of MDMA have a rapid-onset and do not require daily dosing or a steady state in the blood to be effective. Thus, the effects of MDMA are distinct from and go well beyond anxiolytics and SSRIs. Furthermore, there is no evidence that MDMA creates a physical dependency, as benzodiazepines do. Previous studies of polydrug users have found a small percentage of people exhibit problematic use of Ecstasy (material represented as containing MDMA) [29, 30]. Studies of regular or problematic Ecstasy users indicate that on average, regular use occurs no more often than once a week [31]. Hence, MDMA may have moderate abuse potential. See the Investigator’s Brochure (IB) for a more detailed explanation.

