3.3 Safety Objectives

The overall safety objective is to assess differences between groups in severity, incidence and frequency of Adverse Events (AEs), Treatment Emergent AEs (TEAEs), AEs of Special Interest (AESIs), and Serious Adverse Events (SAEs), concomitant medication use, suicidal ideation and behavior, and vital signs to support the package insert for MDMA-assisted psychotherapy. The following safety objectives will evaluate the safety of MDMA-assisted psychotherapy compared to identical psychotherapy with inactive placebo:

1. Compare relative incidence of AEs during Experimental Sessions that may be indicative of a medical complication of the Investigational Medicinal Product (IMP) such as clinical signs and symptoms of chest pain, shortness of breath, or neurological symptoms or any other signs or symptoms that prompt additional vital sign measurements.
2. Compare relative incidence of AEs by severity.
3. Compare relative incidence of TEAEs, to determine relationship to the IMP based on relative incidence in the MDMA group.
4. Compare relative incidence of TEAEs by severity reported during an Experimental Session, 1 day, and 2 days after IMP administration.
5. Compare relative incidence of AESIs, defined as AEs specified in the protocol related to cardiac function and abuse liability.
6. Compare relative incidence of AEs by severity categorized as leading to discontinuation of IMP, resulting in death or hospitalization, and continuing at Study Termination.
7. Compare relative incidence of SAEs.
8. Compare relative incidence of concomitant medications taken during an Experimental Session, 1 day, and 2 days after IMP administration.
9. Compare relative incidence of psychiatric concomitant medications taken during the Treatment Period.
10. Compare relative incidence of positive or serious suicidal ideation and positive suicidal behavior assessed with the Columbia Suicide Severity Rating Scale (C-SSRS) by treatment group.
11. Compare mean changes in blood pressure, heart rate, and body temperature from pre-IMP administration to end of each Experimental Session by treatment group.

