10.2.4.1 Common AEs

Common AEs are typically observed during IMP administration, but are transient and diminish as the IMP is metabolized and excreted over the next 72 hours after dosing. Common AEs most frequently reported during Experimental Sessions include muscle tightness in the jaw, lack of appetite, dizziness, and nausea. During the week following treatment, lack of appetite, muscle tightness in the jaw, restlessness, weakness, dry mouth, thirst, impaired gait/balance, and sensitivity to cold may be reported. Severe anxiety, insomnia, fatigue, and depressed mood are commonly reported in PTSD studies in both placebo and MDMA groups. Common AEs are typically self-limiting. Elevations in anxiety and poor sleep respond to management with short-

acting low dose benzodiazepines (specifically, lorazepam) or sleep aids as needed, per clinical judgment of the site physician.

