14.2.2 Safety Analyses

Safety analyses will confirm safety data with summary tables listing exposure to IMP, unsolicited AEs, concomitant medications, suicidal ideation and behavior, and vital signs overall and by group. If a participant has more than one AE mapped to the same PT, that AE will be reported once using the highest severity. AEs that occur on Day 0 (Experimental Session), Day 1, Day 2 after IMP administration will be presented separately. Compare relative incidence of AEs during Experimental Sessions such as clinical signs and symptoms, such as chest pain, shortness of breath, or neurological symptoms or any other signs or symptoms that may be indicative of a medical complication of the IMP.

Frequency and incidence of concomitant medications will be displayed by generic name, sorted by class, and summarized by treatment group, analysis set, and category. Concomitant medications taken on Day 0 (Experimental Session), Day 1, Day 2 after IMP administration will be presented separately. Any psychiatric concomitant medications will be tabulated by period (Preparatory, Treatment Period, Follow-up Period). Frequency and incidence of positive or serious ideation and suicidal behavior will be presented using descriptive statistics of C-SSRS scores in tabular format. Vital signs (heart rate, blood pressure, and body temperature) for Experimental Sessions will be summarized using descriptive statistics in tabular format listing values at pre-IMP administration, prior to the supplemental dose, and at the end of each Experimental Session by treatment group. Additional details are available in the Statistical Analysis Plan.

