The sponsor and investigators agree that allowing participants who are screened for stable domestic circumstances to return home will not increase the risks of participation in the study. The study protocol discusses the risk of psychological distress in a PTSD population and mitigation in [Section 10.2.2.2](#). Therapists and site physicians are aware of these risks, including anxiety and depressed mood occasionally reported 1 to 3 days after MDMA administration. In previous Phase 1 and 2 studies, these reactions have been transient and have responded well to reassurance from the therapy team, with occasional use of benzodiazepines for anxiety. If needed, the study physician may prescribe a short-acting, low-dose benzodiazepine (specifically, lorazepam) or sleep aids (excluding trazodone) as needed.

Consistent with the main study protocol and the sub-study, proper preparation and follow-up support will reduce the difficulties participants might have with acute or sub-acute reactions. The potential for destabilizing psychological distress will be minimized by:

- Excluding people who might be more vulnerable to it (such as people diagnosed with bipolar affective disorder type 1 or with psychotic disorders)
- Excluding people who do not have a stable living situation or supportive family/network

- Preparatory Sessions of non-drug psychotherapy before the Experimental Session
- Creating an atmosphere of trust during the Experimental Session
- Close monitoring
- Phone contact with participants during the week after the Experimental Session
- Conduct of Integrative Session on the morning after the Experimental Session

Specific to sub-study:

- Therapist phone contact with participants on the night of the Experimental Session.
- A support person identified by the participant and agreed upon by the therapist must stay with the participant overnight on the evening following the Experimental Session.
- The therapists will meet with the support person prior to the first Experimental Session to assess their ability to act as an appropriate support person and to give them instructions about what to expect following Experimental Sessions and how to contact study personnel if needed.

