8.8.2 Analysis of Adverse Events

The primary measure of safety will be the reporting of unsolicited AEs. All AEs collected from Enrollment to Termination will be categorized as follows:

- Pretreatment AEs are defined as AEs that occur during the Preparatory Period prior to the first dose in the first Experimental Session
- Treatment Emergent AEs are defined as AEs that occur during the Treatment Period from the first Experimental Session to the last Integrative Session
- AEs that occur on and two days after MDMA or placebo administration
- AESIs are defined as AEs specified in the protocol related to cardiac function and abuse liability
- Follow-up Period AEs are defined as AEs that occur during the Follow-up Period after the last Integrative Session through Termination
- AEs leading to discontinuation of IP
- AEs resulting in death or hospitalization.
- SAEs
- AEs continuing at Termination.

Verbatim terms on case report forms will be mapped to preferred terms (PT) and system organ class (SOC) using the Medical Dictionary for Regulatory Activities (MedDRA) Version 17.0. Frequency and incidence of AEs will be displayed by PT, sorted by SOC, and summarized by treatment group, analysis set, category (as defined above), severity, and seriousness. AEs will be analyzed and presented as follows:

- If a participant has more than one AE mapped to the same PT, that AE will be reported once using the highest severity
- Relationship will be determined based on relative incidence of TEAEs with at least two-fold difference between MDMA vs. placebo
- Compare relative incidence of AEs during Experimental Sessions such as clinical signs and symptoms, such as chest pain, shortness of breath, or neurological symptoms or any other signs or symptoms that may be indicative of a medical complication of the investigational product
- AEs that occur on day of Experimental Sessions and two days after IP administration will be presented separately.

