8.8.3 Concomitant Medications

A secondary measure of safety will be the reporting of concomitant medications. All concomitant medications collected from Screening to Study Termination will be categorized as follows:

- Pretreatment medications are defined as medications taken prior to and after signing informed consent and those taken during the Preparatory Period prior to the first Experimental Session. A stop date is expected prior to the first Experimental Session for any medications requiring a change in dose, a skipped dose, or tapering.
- Treatment Period concomitant medications are defined as those taken or continued during the Treatment Period from the first Experimental Session to the last Integrative Session. A stop date is expected prior to the each Experimental Session for any medications requiring a change in dose, a skipped dose, or tapering.
- Concomitant medications with a start date of the day of and two days after IP administration
- Follow-up Period concomitant medications are defined as those taken or continued during the Follow-up Period after the last Integrative Session through Termination
- Any concomitant medications that are tapered
- Any concomitant medications that are taken to treat an AE
- Any concomitant medications that are taken to treat an SAE
- Any excluded concomitant medications taken as a deviation from the protocol.

Concomitant medications on case report forms will be classified using the WHO Drug Dictionary Enhanced™ (WHO DDE). Frequency and incidence of concomitant medications will be displayed by generic name, sorted by class, and summarized by treatment group, analysis set, and category as defined above. Concomitant medications will be analyzed and presented as follows:

- Concomitant medications taken on the day of and two days after IP administration will be presented separately
- Any psychiatric concomitant medications by period.

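### The separate post-dose adverse event and medication displays stop at Day 2, although the protocol's own risk section puts reported anxiety and low mood on Days 1 to 3

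*Protocol*

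**What the plan says.** The risk text is in Protocol 10.2.2.2: "Mild anxiety and depressed mood are occasionally reported 1 to 3 days after MDMA administration". Appendix A repeats the interval when it lists the risks that therapists and site physicians know of: "including anxiety and depressed mood occasionally reported 1 to 3 days after MDMA administration".

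The post-dose comparisons use a shorter interval throughout:

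- Safety objective 4 (Protocol synopsis, Protocol 3.3, SAP 3.3) compares treatment-emergent events by severity "reported during an Experimental Session, 1 day, and 2 days after IMP administration". Objective 8 applies the same days to concomitant medications (the synopsis restricts it to psychiatric ones).
- Protocol 14.2.2: "AEs that occur on Day 0 (Experimental Session), Day 1, Day 2 after IMP administration will be presented separately". The next paragraph says the same for medications.
- SAP 8.8.2: "AEs that occur on day of Experimental Sessions and two days after IP administration will be presented separately".
- SAP 8.8.3: "Concomitant medications taken on the day of and two days after IP administration will be presented separately". Its matching category is defined by the medication's start date.

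Neither document gives a reason for stopping at Day 2.

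**The concern.** A display by day after dosing is where an acute or sub-acute drug effect can be told apart from the symptoms of PTSD. Here the display is a day shorter than the interval the protocol gives for the mood after-effect.

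Timing carries more weight than usual in this trial. Under Protocol 11.1 the investigator's opinion on drug relationship is collected only for serious events. For all others, SAP 8.8.2 infers relationship from at least a two-fold difference in treatment-emergent incidence between arms. Those events run from the first Experimental Session to the last Integrative Session, and Protocol 8.3 gives the Treatment Period as 9 to 15 weeks. Protocol 10.2.4.1 says that severe anxiety, insomnia, fatigue and depressed mood are common in PTSD studies in both placebo and MDMA groups. Non-serious anxiety that starts on Day 3 thus gets no individual causality judgment and is pooled with that background. The stated purpose of the safety objectives is to support the package insert.

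**Working it through.** The plan states no figure on this point, so there is none to reproduce. The check compares intervals and traces where a Day 3 onset is reported.

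**1. Days covered.** Risk interval (Protocol 10.2.2.2, Appendix A): {1, 2, 3}. Display interval (objectives 4 and 8, Protocol 14.2.2, SAP 8.8.2 and 8.8.3): {0, 1, 2}. Risk days outside the display: {1, 2, 3} − {0, 1, 2} = {3}. The display covers 2 of the 3 named days.

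**2. Where a Day 3 onset appears.**

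| Item starting on Day 3 | Tables that include it | Day relative to dose shown? |
|---|---|---|
| Adverse event | Treatment-emergent tables by preferred term, arm and severity (SAP 8.8.2) | No |
| Medication | Treatment Period; taken to treat an AE, where that applies; psychiatric medications by period, where that applies (SAP 8.8.3) | No |

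An event or medication that starts on Day 1 or 2 and continues into Day 3 is already in the post-dose display.

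**3. Why pooling hides timing.** Let *b* be background incidence over the Treatment Period, equal in both arms, and *e* the independent probability that MDMA causes the event. Pooled incidence on MDMA is 1 − (1 − b)(1 − e), and the ratio to placebo is 1 + e(1 − b)/b. Both inputs are assumptions; the documents give neither. With e = 20%:

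- b = 10%: 28% v 10%, ratio 2.8
- b = 20%: 36% v 20%, ratio 1.8
- b = 40%: 52% v 40%, ratio 1.3

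The ratio reaches 2 only if b ≤ e/(1 + e), which is 0.20/1.20 = 16.7% here, or 0.10/1.10 = 9.1% with e = 10%. Above 50% on placebo, a two-fold ratio is impossible. This shows why a display by day is useful when the background is common. It does not measure what is missed on Day 3.

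**4. Share starting on Day 3.** The documents give no onset distribution. Even onset over Days 1 to 3 would give 1/3, but that is only an assumption; the possible range is 0 to 100%.

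**5. Effect of extending the display.** Coverage becomes 3 of 3 named days. A participant dosed in three sessions contributes 3 × 4 = 12 display days instead of 3 × 3 = 9.

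**The case against.** **Reported is not onset.** The risk text says when symptoms are reported, not when they start. Many reports on Day 3 may concern events that began earlier and are already counted. This stands, and it is why no share can be put on Day 3.

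**Nothing is lost, and attribution does not use this table.** Day 3 events stay in the treatment-emergent tables, and the two-fold rule runs on those, not on the Day 0 to 2 subset. This also stands. A reader might infer that after-effects drop out of the safety analysis; the documents do not support that. Only the timing display is narrower.

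**The 72-hour statement.** A reader might take Protocol 10.2.4.1 as further proof that Day 2 is too early. It says that common events are "transient and diminish as the IMP is metabolized and excreted over the next 72 hours after dosing". That describes the fading of events typically seen during dosing, which are already counted from Day 0, and a resolution time does not set an onset window. Elimination does not help either. Protocol 2.2.2 states: "Orally administered doses of MDMA have a half-life of 7 to 9 hours in humans". Five half-lives are 5 × 7 = 35 to 5 × 9 = 45 hours. With dosing at about 10:00 (Protocol 8.3.1), Day 2 ends 14 + 48 = 62 hours later, when 0.5^(62/7) = 0.2% to 0.5^(62/9) = 0.8% of the initial dose remains. The argument should not be used.

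**Loss of power.** A reader might turn the missing day into a power loss. That would need assumed incidences, an assumed Day 3 share, and a significance test that the plan does not specify for these displays.

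**Day 3 is no natural boundary.** Protocol 10.2.2.2 allows for distress even later, and 10.2.4.1 lists reactions in the week after treatment. There is also no Day 3 call: Protocol 8.3.2 schedules calls on Days 2, 4 and onward, so some onset dates will rest on recall. Both points are fair. Day 3 is still the end of the only interval the protocol gives for these mood symptoms.

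**Purpose of the tables.** The documents do not say that the Day 0 to 2 displays are meant to show mood after-effects. That is an inference from their post-dose design, though a reasonable one.

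**Conclusion.** The mismatch is in the text: the stated reporting interval is Days 1 to 3, and the separate displays cover Days 0 to 2. Its size is one of three named days. The number of events affected cannot be known from the documents.

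The consequence is limited to visibility. The timing of a Day 3 onset is not shown in any planned summary table, in a trial that collects no investigator causality for non-serious events and expects similar symptoms in both arms. The displays are descriptive; the two-fold rule, primary inference, alpha and sample size do not depend on them. This is a cheap improvement of low severity. The conclusion rests on reading the risk text as the period in which the sponsor expects these symptoms, and on the inference that a post-dose display should cover that period.

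**What to change.** In safety objectives 4 and 8 (Protocol synopsis, Protocol 3.3, SAP 3.3), Protocol 14.2.2, and SAP 8.8.2 and 8.8.3, extend the separate adverse event and medication displays to Day 3. In SAP 8.8.3, extend the start-date category to match. Show Day 3 as its own column so that the Day 0 to 2 window can still be read.

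The cost is one column per display. No new data or visits are needed: start dates are already collected, and the Day 4 call asks about both events and medications. A footnote should say that Day 3 has no scheduled call, so some onset dates rest on recall at Day 4 or at the second Integrative Session.
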